Appendix 1.2. Missing/Incomplete AE Stop Date

If needed, the following imputation rules apply to the case where the end date is incomplete (i.e., partially missing) for adverse events. Other partial end dates will not be imputed. If the imputed stop date is before the start date (imputed or non-imputed start date), then the imputed stop date will be replaced with the start date.

• Missing day and month, or Missing month only

Confidential Page 39 of 56

December 31 will be assigned to the missing fields. If the imputed stop date is after the date of death, date of death will be used.

• Missing day only

If the month and year of the incomplete stop date are the same as the month and year of the last dose date of double-blind study treatment, then the day of the last dose date will be assigned to the missing day.

If the month and year of the incomplete stop date are different from the month and year of the last dose date of double-blind study treatment, then the minimum of (the last day of the month, end of study date, date of death) will be assigned to the missing day.

Missing year

No imputation.

Appendix 1.3. Missing/Incomplete Prior or Concomitant Medication Start Date

Same imputation rules as missing/incomplete AE onset date (Appendix 1.1).

Appendix 1.4. Missing/Incomplete Prior or Concomitant Medication Stop Date

Same imputation rules as missing/incomplete AE stop date (Appendix 1.2).

Appendix 1.5. Missing Date Imputation for Last Dose Date

Imputed last dose date = the earliest date of (last drug dispense date + the number of days of drug dispensed, date of death, date of end of treatment (EOT)/EOS visit, and other dates as appropriate).

Confidential Page 40 of 56

APPENDIX 2. ANALYSIS VISIT WINDOWS

Analysis visits are defined by the windows that will have the widths of the corresponding assessments centered at the scheduled time. Unscheduled visits within a visit window defined below will be grouped into the closest scheduled visits based on the visit date.

Table 6: Analysis Visit Window for Vital Signs

Analysis Visit	Target Day	Start Day	End Day	
Baseline		Last value before the first study drug (or randomization date if no infusion		
Day 1 postdose	1	1	1	
Week 3 (predose and postdose)	22	2	32	
Week 6 (predose and postdose)	43	33	53	
Week 9 (predose and postdose)	64	54	74	
Week 12 (predose and postdose)	85	75	95	
Week 15 (predose and postdose)	106	96	116	
Week 18 (predose and postdose)	127	117	137	
Week 21 (predose and postdose)	148	138	158	
Week 24 (predose and postdose)	169	159	179	
Week 27 (predose and postdose)	190	180	200	
Week 30 (predose and postdose)	211	201	221	
Week 33 (predose and postdose)	232	222	242	
Week 36 (predose and postdose)	253	243	263	
Week 39 (predose and postdose)	274	264	284	
Week 42 (predose and postdose)	295	285	305	
Week 45 (predose and postdose)	316	306	326	
Week 48 (predose and postdose)	337	327	351 [\$] or *[@]	
28 Days post last dose [\$]	365	Date of Last dosing+15 [\$]	* [\$]	

^{\$} For subjects who do not enroll OLE only.

Note: The study day with infusions will be used for summary tables whenever possible.

Note: If raw data shows visit is "28 Days post last dose", then set analysis visit=visit

Note: all assessments beyond 60 days post last infusion will be excluded from summary tables or figures.

Confidential Page 41 of 56

^{*} End of the double-blind period (DBP).

[@] For subjects who enroll OLE.

Table 7: Analysis Visit Window for PFT

Analysis Visit	Target Day	Start Day	End Day
Baseline	Last BTR PFT before the first study drug infusion (or randomization date if no infusion received)		
Week 6	43	2	64
Week 12	85	65	106
Week 18	127	107	148
Week 24	169	149	211
Week 36	253	212	295
Week 48	337	296	End of DBP

Table 8: Analysis Visit Window for HRCT

Analysis Visit	Target Day	Start Day	End Day
Baseline	Last value before the first study drug infusion (or randomization date if no infusion received)		
Week 24	169	2	253
Week 48	337	254	End of DBP

Table 9: Analysis Visit Window for Labs

Analysis Visit	Target Day	Start Day	End Day
Baseline	Last value before the first study drug infusion (or randomization date if no infusion received)		
Week 12	85	2	127
Week 24	169	128	211
Week 36	253	212	295
Week 48	337	296	351 [\$] or *[@]
28 days after last dose [\$]	365	Date of Last dosing+15 [\$]	* [\$]

^{\$} For subjects who do not enroll OLE only.

Note: If raw data shows visit is "28 Days post last dose", then set analysis visit=visit

Note: all assessments beyond 60 days post last infusion will be excluded from summary tables for labs.

Confidential Page 42 of 56

^{*} End of the double-blind period.

[@] For subjects who enroll OLE.

Table 10: Analysis Visit Window for SGRQ, UCSD-SOBQ, LCQ, PE, and Weight

Analysis Visit	Target Day	Start Day	End Day	
Baseline	Last value before the first study	alue before the first study drug infusion (or randomization date if no infusion received)		
Week 12	85	2	127	
Week 24	169	128	211	
Week 36	253	212	295	
Week 48	337	296	End of DBP	

Note: all assessments beyond 60 days post last infusion will be excluded from summary tables for PE.

Table 11: Analysis Visit Window for ECG

Analysis Visit	Target Day	Start Day	End Day
Baseline	Last value before the first study drug infusion (or randomization date if no infusion received)		
Week 48	337	2	End of DBP

Note: all assessments beyond 60 days post last infusion will be excluded from summary tables for ECG.

Table 12: Analysis Visit Window for Biomarkers (Serum and Plasma)

Analysis Visit	Target Day	Start Day	End Day
Day 1	1	1	1
Week 24	169	2	253
Week 48	337	254	351 [\$] or *[@]
28 days Post last dose [\$]	365	Date of Last dosing+15 [\$]	* [\$]

^{\$} For subjects who do not enroll OLE only.

Note: If raw data shows visit is "28 Days post last dose", then set analysis visit=visit

Note: all assessments beyond 60 days post last infusion will be excluded from summary tables.

Confidential Page 43 of 56

^{*} End of the double-blind period.

[@] For subjects who enroll OLE.

Table 13: Analysis Visit Window for CTGF and ADA (Plasma)

Analysis Visit	Target Day	Start Day	End Day
Day 1	1	1	1
Week 24	169	2	211
Week 36	253	212	295
Week 48	337	296	351 [\$] or *[@]
28 days Post last dose [\$]	365	Date of Last dosing+15 [\$]	* [\$]

^{\$} For subjects who do not enroll OLE only.

Note: If raw data shows visit is "28 Days post last dose", then set analysis visit=visit

Note: all assessments beyond 60 days post last infusion will be included in summary tables.

Table 14: Analysis Visit Window for Pharmacokinetic Concentration (Plasma)

Analysis Visit	Target Day	Start Day	End Day
Day 1	1	1	1
Day 8	8	2	11
Day 15	15	12	18
Week 3	22	19	52
Week 12	85	53	127
Week 24	169	128	211
Week 36	253	212	295
Week 48	337	296	351 [\$] or *[@]
28 days Post last dose [\$]	365	Date of Last dosing+15 [\$]	* [\$]

^{\$} For subjects who do not enroll OLE only.

Note: If raw data shows visit is "28 Days post last dose", then set analysis visit=visit

Note: all assessments beyond 60 days post last infusion will be included in summary tables.

Confidential Page 44 of 56

^{*} End of the double-blind period.

[@] For subjects who enroll OLE.

^{*} End of the double-blind period.

[@] For subjects who enroll OLE.

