3.4. Study Periods

[figure not shown]
This study consists of the following study periods (Figure 1):

- Main (double-blind, placebo-controlled) study period:
 - Screening period: Up to 6 weeks
 - Treatment period: 48 weeks
- Optional, open label extension (OLE) period:

Access to pamrevlumab during the OLE period will be available until the last enrolled subject completes 48 weeks of treatment in the OLE period, or pamrevlumab is commercially available for the indication of IPF, or the Sponsor decides to end the OLE period, whichever occurs first.

- Follow-up period/final safety assessment:
 - 28 days after the last dose: scheduled visit
 - 60 days after the last dose: follow-up phone call, for a final safety assessment

Figure 1: Study Schema

The intent for this study is to evaluate the efficacy and safety profile of pamrevlumab as monotherapy in subjects with IPF who were previously treated with an approved therapy but

Confidential Page 13 of 56

who discontinued that therapy (possible reasons for discontinuation of approved therapy could include, but are not limited to, intolerance or disease progression), unless neither treatment is available in the host country.

After randomization and during the treatment period, co-administration of an approved IPF therapy (i.e., pirfenidone or nintedanib) is permitted if clinically indicated in the Investigator's opinion, provided that the Investigator assesses the potential risks/benefits of combining approved IPF therapies with blinded study treatment.

Subjects who complete the Week 48 visit of the main study (regardless of the number of study drug infusions received and or treatment group assigned in the double-blind period) will be eligible to participate in the optional OLE period of the study that offers continuing access to pamrevlumab regardless of randomization assignment in the main study.

Subjects who discontinue study treatment for any reason are encouraged to remain in the study and be followed for all study visits and assessments.

The following assessments will be assessed centrally by independent external vendors or study committees:

- Pulmonary function tests (PFTs)
- High-resolution computed tomography (HRCT)
- Acute IPF exacerbations and respiratory hospitalizations

In addition, an independent Data Monitoring Committee (DMC) will review safety data and other clinical data (with the authority to unblind such data) on a periodic basis to monitor overall subject safety.

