5.3. General Data Handling Rules and Presentation Specifications

5.3.1. Analysis Period

5.3.1.1. On-Study Period

Unless otherwise specified, the efficacy analysis will be based on the on-study period, which includes all data collected during the double-blind period.

For the safety analysis, all safety assessments beyond 60 days of the last dose will be excluded from summary tables or figures.

Confidential Page 17 of 56

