5.5. Analysis Visit Window

Analysis visits, instead of the nominal visits from case report form (CRF), derived from visit dates and visit time windows will be used in the by-visit analyses. Unscheduled visits within a visit window (defined in Appendix 2) will be grouped into the closest scheduled visits based on the visit date. For subjects who have more than one measurement at a certain analysis visit, the last measurement will be used, with the following exceptions:

- Liver function tests, such as Alanine Aminotransferase (ALT), Aspartate Aminotransferase (AST), Gamma-Glutamyltransferase (GGT), Alkaline Phosphatase (ALP), and total bilirubin, in which the maximum value will be used.
- Spirometry data: the best value to be used for analysis as defined in Section 5.1.4.
- Vital signs: the values on the infusion days will be used if applicable.
- ADA assessment: select in the order of 1) last ADA+ assessment; 2) earlier ADA+ assessment; 3) last ADA- assessment.

Confidential Page 19 of 56

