6.10.3. Clinical Implication of ADA Immune Response

6.10.3.1. PK

• Effect of ADA response on drug exposure will be explored by examining the drug exposures using graphical plots or simple summary statistics of observed drug concentration levels by ADA status and sampling time. Corresponding numerical values of geometric mean, arithmetic mean, and standard deviation will be displayed under the figures.

Confidential Page 36 of 56

• A listing of drug concentrations will be provided. Time course of observed concentrations by study visit with identifiers for antibody response will be plotted for each subject separately.

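### PK and CTGF samples taken more than 60 days after the last infusion enter the by-visit summaries, so those rows, and concentration by ADA status, mix on-drug with off-drug values

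*SAP*

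**What the plan says.** In the double-blind SAP, Appendix 2, the notes to Table 13 (CTGF and ADA) and Table 14 (PK concentration) both state that "all assessments beyond 60 days post last infusion will be included in summary tables". The note to Table 12 (other biomarkers) states that "all assessments beyond 60 days post last infusion will be excluded from summary tables". The notes for vital signs, laboratory tests, physical examination and ECG also exclude late assessments. No reason is given for the difference.

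Section 5.5 assigns analysis visits by study day: visits "derived from visit dates and visit time windows will be used in the by-visit analyses". It adds: "For subjects who have more than one measurement at a certain analysis visit, the last measurement will be used". PK and CTGF are not among the listed exceptions. Section 3.4 says: "Subjects who discontinue study treatment for any reason are encouraged to remain in the study and be followed for all study visits and assessments".

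Section 6.10.3.1 explores the effect of ADA on exposure through plots or "simple summary statistics of observed drug concentration levels by ADA status and sampling time", reporting geometric and arithmetic means. It sets no condition on time since the last infusion. Section 5.3.1.2 defines an on-treatment period (within 3 weeks of the last infusion), but nothing applies it to PK or CTGF.

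**The concern.** A concentration summary labelled Week 24, 36 or 48 will be read as exposure on 30 mg/kg every 3 weeks. If some of the values come from subjects who stopped months earlier, the row mixes exposure with discontinuation. The geometric mean is the most exposed, because a few near-zero values pull it down sharply. Under SAP 5.3.4 a result reported as below a limit is entered at that limit, so such values stay in the calculation.

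Two readings are at stake. The first is the concentration by visit. The second is the comparison by ADA status: if ADA-positive and ADA-negative subjects stop drug at different rates, the groups will differ in mean concentration even if antibodies do nothing to clearance. For CTGF, on-drug and off-drug values are pooled under a rule opposite to that for the other biomarkers, although Section 4.5 lists them together.

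**Working it through.** The plan states no figure for this point, so there is none to reproduce. The check has three parts.

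**1. Can such samples occur?** Target days follow 7 x week + 1: 85, 169, 253 and 337 for Weeks 12, 24, 36 and 48, as in Table 14. Infusions fall every 21 days from Day 1. A target-day sample is more than 60 days after the last infusion in these cases:

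| Sample | Target day | Latest last infusion | Gap |
|---|---|---|---|
| Week 12 (PK only) | 85 | Week 3, Day 22 | 63 days |
| Week 24 | 169 | Week 15, Day 106 | 63 days |
| Week 36 | 253 | Week 27, Day 190 | 63 days |
| Week 48 | 337 | Week 39, Day 274 | 63 days |

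A subject last dosed at Week 12 (Day 85) who stays gives Week 24, 36 and 48 samples 84, 168 and 252 days off drug.

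**2. Which row do they enter?** A subject can enter the OLE after completing Week 48, "regardless of the number of study drug infusions received". For OLE entrants the row for 28 days post last dose does not apply, so late samples fall in the Week rows. For subjects not entering the OLE, that row's window runs from last dose + 15 days to the end of the double-blind period and overlaps the later Week windows. A note sends samples labelled as the 28-day visit to that row, but nothing says where other samples in the overlap go. In the example the window opens on Day 100, so all three later samples satisfy two windows. Under the last-measurement rule, one taken 252 days off drug could stand for day 28.

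**3. How large is the effect?** Assumptions, none of them in the documents: half-life t = 10 to 20 days; share of sampled subjects off drug p = 5% to 20%; off-drug level f as a fraction of the 21-day trough.

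- Washout: f = 2^(-(d - 21)/t), with d in days since the last infusion. At d = 60 and t = 20, f = 2^(-1.95) = 0.26. At d = 120 and t = 10, f = 2^(-9.9) = 0.001. The range used below stops at 1%; a lower residual would deepen the fall in the geometric mean.
- Arithmetic mean relative to all on drug: 1 - p(1 - f).
- Geometric mean relative to all on drug: f^p.

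| p | f | Arithmetic factor | Geometric factor |
|---|---|---|---|
| 5% | 0.26 | 0.96 | 0.93 |
| 5% | 0.01 | 0.95 | 0.79 |
| 20% | 0.26 | 0.85 | 0.76 |
| 20% | 0.01 | 0.80 | 0.40 |

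The arithmetic mean therefore falls by about 4-20% and the geometric mean by about 7-60%.

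For ADA status with no true antibody effect, the ratio of geometric means is f^(p1 - p0), where p1 and p0 are the off-drug shares in ADA-positive and ADA-negative subjects. Equal shares give 1.00. Hypothetical shares of 20% and 10% give f^0.10, that is 0.87 (f = 0.26) to 0.63 (f = 0.01).

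Reversing the 60-day note alone would leave samples 22 to 60 days off drug. At day 60 the level is 2^(-3.9) = 0.07 (t = 10) to 0.26 (t = 20) of trough, so PK needs a further on-drug condition.

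**The case against.** The case for leaving the plan alone has several parts.

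- **Inclusion follows a general rule.** SAP 5.3.5 considers all collected assessments, on or off treatment. The 60-day rule in 5.3.1.1 reads "For the safety analysis, all safety assessments beyond 60 days of the last dose will be excluded from summary tables or figures", and PK and CTGF are not among the safety assessments in Section 4.4. This stands: including late PK and CTGF samples does not breach 5.3.1.1. It does not make the rows valid as exposure summaries.
- **The 20% planning figure is the wrong proxy.** A reader might take the sample-size dropout allowance as the off-drug share. The documents do not support that. Under protocol 4.4, subjects who withdraw get an early termination visit, a 28-day visit and phone calls, so they do not supply later visit samples. The relevant group stopped infusions, stayed in the study and, for PK, consented to the optional sampling. Its size is unknown, hence the range from 5%.
- **The antibody artefact is conditional.** A reader might infer that the ADA comparison will show a false effect. That requires stopping to differ by ADA status, and nothing in the documents shows that it does.
- **The consequence is small.** PK is an optional subset, the ADA comparison is exploratory and untested, listings and per-subject time courses with antibody identifiers are planned, and population PK has its own plan. All of this stands and limits the severity.
- **A tight cutoff would harm good data.** Visits are scheduled from Day 1 with a window of 7 days either side, so two in-window infusions can be 21 + 7 + 7 = 35 days apart. A 21- or 28-day cap would drop valid troughs. A 28-day cap would also remove samples from days 29-35 of the scheduled 28-day post-dose visit. This stands and shapes the fix.

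**Conclusion.** The point holds as a flaw in the summary rules. Tables 13 and 14 admit washed-out PK and CTGF samples to scheduled rows, and nothing in 6.10.3.1 removes them from the comparison by ADA status. Which row receives them is certain only for OLE entrants; for others it may be the overlapping 28-day row.

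The size of the PK shift rests wholly on the assumed off-drug share, residual level and half-life. For CTGF no size can be given, because the documents provide no on-drug and off-drug levels. Late samples are defensible for ADA detection, which shares Table 13. The effect is confined to exploratory PK, ADA and CTGF summaries. The change is worth making because it is cheap and the rows would otherwise be mislabelled.

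**What to change.** - In Table 14, and for CTGF only in Table 13, change included to excluded for samples more than 60 days after the last infusion.
- For the PK Week rows and the concentration summaries by ADA status in 6.10.3.1, use only samples from subjects still being dosed, for example within 35 days of the last infusion (21 days plus the two 7-day visit windows).
- Exempt the scheduled row for 28 days post last dose from that condition, and limit it to the nominal visit, which also settles the overlap with the Week rows.
- Keep later samples in the listings and per-subject time-course plots, shown by time since last infusion.
- Keep late samples for ADA. Because Section 4.4 lists immunogenicity as a safety assessment, state this as an exception to 5.3.1.1.

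The cost is SAP wording and a filter in the PK and CTGF tables. Visit rows will hold somewhat fewer samples, including some from subjects who missed an infusion and later resumed. No data leave the listings.

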APPENDIX 3. SGRQ

The SGRQ is designed to measure health impairment in patients with asthma and COPD. It is also valid for use in bronchiectasis and has been used successfully in patients with kyphoscoliosis and sarcoidosis. It includes Symptoms scores (questions 1-8), Activity scores (questions 11 and 15), and Impacts scores (questions 9-10, 12-14, and 16-17). A Total score is also calculated which summarizes the impact of the disease on overall health status. Scores are expressed as a percentage of overall impairment where 100 represents the worst possible health status and 0 indicates the best possible health status.

Questions 1-7, 9, 10 &17 Where a patient has ticked a box, a value of 1 is entered for the appropriate question. The empty boxes are entered as 0. It will be noted that the questionnaire requests a single response to questions 1-7, 9-10, and 17. If multiple responses are given to one of these questions, then averaging the weights for the positive responses for that question is acceptable.

Question 8 Where a patient has ticked 'Yes' to having a worse wheeze in the morning, a value of 1 is entered for the appropriate question. All other responses are entered as 0.

Questions 11 - 16 Where a patient has ticked 'True', a value of 1 is entered for the appropriate question, and where a patient has ticked 'False' a value of 0 is entered. Where a patient has missed a question the cell on the spreadsheet is left blank. In response to question 14, if a patient is not receiving medication, then the response is zero, otherwise, the values are missing.

Missing Questions

The missing (blanks) in part 1 (Symptoms) will be imputed by an average of the multiple weighted responses in part 1. This imputation will adjust for up to 24% of missing items in the questionnaire. If more than 24% of items are missing, the component score will be 'Missing'.

Missed Items for Component Scores

It is better not to miss items and any missing items are the fault of the experimenter, not the patient. The effect of missing items and recommendations from the scoring manual are the following:

Symptoms Score: The Symptoms component will tolerate a maximum of 2 missed items from questions 1-8.

Activity Score: The Activity component will tolerate a maximum of 4 missed items from questions 11 and 15.

Impacts Score: The Impacts component will tolerate a maximum of 6 missed items from questions 9-10, 12-14, and 16-17.

Therefore, if there are more than the recommended missed items described above the component score will be set to missing. If one of the component scores is missing, then the total score is missing.

Outline of Scoring Algorithm

• Principle of calculation

Confidential Page 45 of 56

Each questionnaire response has a unique empirically derived 'weight'. The lowest possible 'weight' is zero and the highest 'weight' is 100.

- Each component of the questionnaire is scored separately in three steps:
 - The weights for all items with positive responses are summed.
 - The weights for missed items are deducted from the maximum possible weight for each component. The weights for all missed items are deducted from the maximum possible weight for the Total score.

Sum of maximum possible weights for each component and Total:

Component	Questions	# of tolerated	Maximum
		maximum missing items	Possible Weight
Symptoms	1 – 8	2	662.5
Activity	11 and 15	4	1209.1
Impacts	9-10, 12-14, 16-17	6	2117.8
Total	All		3989.4

(Note: these are the maximum possible weights that could be obtained for the worst possible state of the patient).

 The score is calculated by dividing the summed weights by the adjusted maximum possible weight for that component and expressing the result as a percentage:

Score = 100% x (Summed weights from positive items in that component/Sum of weights for all items in that component)

The Total score is calculated similarly:

Score = $100 \times (Summed weights from positive items in the questionnaire/Sum of weights for all items in the questionnaire)$

Item Weights

The following weights will be used to score the answers similar to the Excel-based system and other computerized scoring systems. Note that the wording of the item may not correspond exactly with the wording in the current version of the questionnaire.

PART 1

1) Over the past 3 months, I have coughed:

1) 5 for the buse of months, I have cought at	
Response	Weight
almost every day	80.6
several days a week	63.2
a few days a month	29.3
only with respiratory infections	28.1
not at all	0.0

2) Over the past 3 months, I have brought up phlegm (sputum):

Confidential Page 46 of 56

Response	Weight
almost every day	76.8
several days a week	60.0
a few days a month	34.0
only with respiratory infections	30.2
not at all	0.0

3) Over the past 3 months, I have had shortness of breath:

Response	Weight
almost every day	87.2
several days a week	71.4
a few days a month	43.7
only with respiratory infections	35.7
not at all	0.0

4) Over the past 3 months, I have had wheezing attacks:

Response	Weight
almost every day	86.2
several days a week	71.0
a few days a month	45.6
only with respiratory infections	36.4
not at all	0.0

5) How many times during the past 3 months have you suffered from severe or very unpleasant respiratory attacks?

Response	Weight
more than 3 times	86.7
3 times	73.5
2 times	60.3
1 time	44.2
none of the time	0.0

6) How long did the worst attack of chest trouble last?

Response	Weight
a week or more	89.7
3 or more days	73.5
1 or 2 days	58.8
less than a day	41.9

7) Over the past 3 months, in a typical week, how many good days (with few respiratory problems) have you had?

Response	Weight
No good days	93.3
1 or 2 good days	76.6
3 or 4 good days	61.5
nearly every day was good	15.4
every day was good	0.0

Confidential Page 47 of 56

8) If you wheeze, is it worse when you get up in the morning?

Response	Weight
No	0.0
Yes	62.0

• PART 2

9) How would you describe your respiratory condition?

Response	Weight
The most important problem I have	83.2
Causes me quite a lot of problem	82.5
Causes me a few problems	34.6
Causes no problem	0.0

10) If you have ever held a job:

Response	Weight
My respiratory problems made me stop working altogether	88.9
My respiratory problems interfere with my job or made me change my job	77.6
My respiratory problems do not affect my job	0.0

11) Questions about what activities usually make you feel short of breath these days.

Response	Weight
Sitting or lying still	90.6
Washing or dressing yourself	82.8
Walking around the house	80.2
Walking outside on level ground	81.4
Walking up a flight of stairs	76.1
Walking up hills	75.1
Playing sports or other physical activities	72.1

12) More questions about your cough and shortness of breath these days.

Response	Weight
Coughing hurts	81.1
Coughing makes me tired	79.1
I am short of breath when I talk	84.5
I am short of breath when I bend over	76.8
My coughing or breathing disturbs my sleep	87.9
I get exhausted easily	84.0

13) Questions about other effects your respiratory problems may have on you these days.

Response	Weight
My cough or breathing is embarrassing in public	74.1
My chest trouble is a nuisance to my family friends or neighbors	79.1
I get afraid or panic when I cannot catch my breath	87.7
I feel that I am not in control of my respiratory problems	90.1
I do not expect my respiratory problems to get any better	82.3
I have become frail or an invalid because of my respiratory problems	89.9

Confidential Page 48 of 56

Exercise is not safe for me	75.7
Everything seems too much of an effort	84.5

14) Questions about your respiratory treatment.

Response	Weight
My treatment does not help me very much	88.2
I get embarrassed using my medication in public	53.9
I have unpleasant side effects from my medication	81.1
My medication interferes with my life a lot	70.3

15) Questions about how activities may be affected by your breathing.

Response	Weight
I take a long time to get washed or dressed	74.2
I cannot take a bath or shower, or I take a long time to do it	81.0
I walk slower than other people my age, or I stop to rest	71.7
Jobs such as household chores take a long time, or I have to stop to rest	70.6
If I walk up one flight of stairs, I have to go slowly or stop	71.6
If I hurry or walk fast, I have to stop or slow down	72.3
My breathing makes it difficult to do things such as walk-up hills, carry things upstairs, light gardening such as weeding, dance, bowl or play golf	74.5
My breathing makes it difficult to do things such as carry heavy loads, dig in the garden or shovel snow, jog or walk briskly (5 miles per hour), play tennis or swim	71.4
My breathing makes it difficult to do things such as very heavy manual work, ride a bike, run, swim fast, or play competitive sports	63.5

16) We would like to know how your respiratory problems usually affect your daily life.

Response	Weight
I cannot play sports or do other physical activities	64.8
I cannot go out for entertainment or recreation	79.8
I cannot go out of the house to do the shopping	81.0
I cannot do housework chores	79.1
I cannot move far from my bed or chair	94.0

17) Tick the statement which you think best describes how your chest affects you.

Response	Weight
It does not stop me from doing anything I would like to do	0.0
It stops me from doing one or two things I would like to do	42.0
It stops me from doing most of the things I would like to do	84.2
It stops me from doing everything I would like to do	96.7

Confidential Page 49 of 56

